#### 10.2.3. Number of days of use of concomitant treatments in each group

The number of days of use of concomitant treatments, that may affect common cold symptoms, in each group will be compared by means of chi-square or exact Fisher test. Subjects will be analysed on the FAS.

The treatments that may affect common cold symptoms are antipyretics, systemic or local mucolytics, decongestants, antitussives and antibiotics.

The number of days of use of these medications is defined as follows:

- A day is counted when the patient used at least one of these medications this day;
- Each day is counted once, whatever the number of these medications used this day;
- The total number is the sum of all distinct days of use of these medications, from D1 to D15.

The same analysis will be performed for each category of medications: antipyretics, systemic or local mucolytics, decongestants, antitussives and antibiotics.

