### **8.4 Secondary endpoints**

-The analysis of the primary endpoint will be completed by an analysis of the AUC for each of the WURSS-21 components (symptoms and Quality-of-Life).

-Duration endpoints will be summarized using the medians, with 95% CIs for the medians by group. Results for Healsea® Rescue\* group and Placebo group will be compared using Wilcoxon-Mann-Whitney test.

-The number of days of use of concomitant treatments in each group will be compared by means of chi-square test or exact Fisher test.

-The subject general satisfaction in each group will be compared by means of chi-square test. And the global subject feedback on treatment use in each group will be compared by means of exact Fisher test.

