### 2.2. Secondary objectives

The secondary objectives are:

- To compare the efficacy of Healsea® Rescue\* and of the Placebo to reduce the duration of each infectious rhinitis symptoms rated by the short version of the Wisconsin Upper Respiratory Symptom Survey (WURSS-21);
- To compare the efficacy of Healsea® Rescue\* and of the Placebo to reduce the use of concomitant medication (antipyretics, systemic or local mucolytics, decongestants, antitussives, antibiotics);
- To compare the subject overall assessment on efficacy of Healsea® Rescue\* and of the Placebo;
- Safety: to assess systemic and local tolerance of Healsea® Rescue\* over the study period.

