### 6.2. Description

The number of available data and the number of missing data will be given and the following descriptive statistics will be provided:

- For quantitative parameters: mean, standard deviation, median, Q1, Q3, extreme values (min and max).

In this case, calculated statistics (mean, standard deviation, median, Q1, Q3) will generally be displayed with one more significant figure than the observed data, unless the described variable necessitates less precision.

- For qualitative parameters: number and percentage of each modality.

Usually, one decimal digit will be given. A second decimal digit could be provided to improve the display, if required.

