### 6.3. Statistical/Analytical issues

#### 6.3.1. Significance level

All statistical analyses will be performed at the 0.05 global significance level (type I error rate), using one-sided tests.

The statistical results are conclusive for the primary efficacy criterion.

All the other statistical results have to be considered within a descriptive perspective and not as inferential issues. No adjustment for Type I error is done. P-values of statistical tests will be provided for information only.

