### 8.4. Symptom's score of acute rhinitis

Symptoms' scores of acute infectious rhinitis will be described at baseline.

For each symptom's score, a Student (or Wilcoxon if the normality assumption is not acceptable) between-groups test will be performed.

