**Figure 14.2.X.X. Boxplots of XXX by treatment group – XXX Set**

**Table 14.2.2.3.X. Number of days of use of XXX in each group – Full Analysis Set**

	Healsea Rescue N=XX	Placebo N=XX
Number of days of intakes of XXX		
N	XX	XX
Missing	XX	XX
0	XX.X (XX.X%)	XX.X (XX.X%)
1	XX.X (XX.X%)	XX.X (XX.X%)
2	XX.X (XX.X%)	XX.X (XX.X%)
...	XX.X (XX.X%)	XX.X (XX.X%)
Between-groups test	XXX (Chi-2/Fisher)	

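### Days of cold-medication use are an ordered count, but the plan compares them with an unordered chi-square or Fisher test that ignores order and has no one-sided form

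*SAP*

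**What the plan says.** SAP 10.2.3 defines a whole number for each subject: the distinct days, from D1 to D15, on which at least one listed cold medicine was taken. It then states that treatments "that may affect common cold symptoms, in each group will be compared by means of chi-square or exact Fisher test", and repeats the analysis for each of five drug classes, which makes six tables. Protocol 8.4 agrees: "The number of days of use of concomitant treatments in each group will be compared by means of chi-square test or exact Fisher test".

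Mock table 14.2.2.3.X settles how this is done. Under "Number of days of intakes of XXX" it has rows 0, 1, 2 and so on, with one Chi-2/Fisher result for the whole table. This is not a comparison of any use with none. The table shows no mean, median or between-group difference.

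Three other statements bear on the choice:

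- The objective (SAP 2.2) has a direction: "to reduce the use of concomitant medication (antipyretics, systemic or local mucolytics, decongestants, antitussives, antibiotics", among other aims.
- SAP 6.3.1 places all analyses "at the 0.05 global significance level (type I error rate), using one-sided tests". For everything except the primary criterion it adds: "P-values of statistical tests will be provided for information only".
- Elsewhere the SAP treats similar data as ordered. Symptom duration, also in days, gets a Wilcoxon-Mann-Whitney test (10.2.2). For the baseline symptom scores, which have only the levels 0 to 3 (protocol 7.4.1, Visit 1), "a Student (or Wilcoxon if the normality assumption is not acceptable) between-groups test will be performed" (SAP 8.4).

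**The concern.** A chi-square or Fisher (Freeman-Halton) test on a table with more than two rows asks only whether the two arms differ in some way across the rows. It does not know that 5 days is more than 1 day. Three consequences follow.

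- The p-value ignores the order of the days.
- It has no one-sided form, so it cannot follow SAP 6.3.1.
- It does not answer whether use fell, which is the stated objective.

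Spreading the comparison over many rows also tends to cost power. At stake is a p-value that speaks to the objective and, since the table carries no estimate, a direct statement of how large any reduction was.

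**Working it through.** **No figure to reproduce.** The documents give no distribution, power or sample size for medication days. The number per arm below is borrowed from the primary endpoint: 180/2 = 90 evaluable per arm, with 180/(1 − 0.10) = 200 randomised.

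**1. What the test uses.** Take an invented table with 90 per arm and days 0 to 5. Device: 30, 25, 15, 10, 6, 4 (mean 129/90 = 1.43 days). Placebo: 20, 20, 16, 14, 11, 9 (mean 183/90 = 2.03 days). With equal arms, chi-square = Σ(a − b)²/(a + b) = 100/50 + 25/45 + 1/31 + 16/24 + 25/17 + 25/13 = 6.65 on 5 df.

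| Data | Chi-square p | One-sided Wilcoxon p |
|---|---|---|
| As above | 0.248 | 0.006 |
| Arms swapped | 0.248 | 0.994 |
| Day labels scrambled | 0.248 | 0.341 |

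The last row is the telling one. Any two-sided p-value survives swapping the arms, but a test of a day count should not survive scrambling the days. This result needs no assumption about the trial's data.

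**2. Power under assumed distributions.** Assumed placebo: 35% non-users; users' days = 1 + negative binomial (size 1.5), user mean 4.0, capped at 15. Mean use is (1 − 0.35) × 4.0 = 2.6 days. Device arm (share of non-users, user mean):

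- general fall: 0.45, 3.3, so 0.55 × 3.3 = 1.8
- larger general fall: 0.50, 2.8, so 1.4
- fewer users only: 0.52, 4.0, so 1.9
- fewer days among users only: 0.35, 2.9, so 1.9

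There were 3,000 replicates, each test at 0.05.

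| Scenario | Chi-square | Fisher | Wilcoxon, two-sided | Wilcoxon, one-sided |
|---|---|---|---|---|
| No effect | 3% | 5% | 4% | 5% |
| General fall, 2.6 to 1.8 | 11% | 17% | 44% | 56% |
| General fall, 2.6 to 1.4 | 34% | 42% | 80% | 88% |
| Fewer users only | 22% | 31% | 53% | 65% |
| Fewer days among users only | 15% | 20% | 20% | 29% |
| Device worse (1.4 placebo, 2.6 device) | 32% | 41% | 80% | 0% |
| One class, 20% v 10% users | 10% | 22% | 47% | 58% |
| One class, 2% v 1% users | 0% | 0.5% | 5% | 12% |

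The like-for-like comparison is Fisher against two-sided Wilcoxon; the last column also gains from being one-sided. The overall-use tables averaged 12 to 14 occupied rows. In every replicate more than 20% of expected counts were below 5, so Fisher would usually be the test applied.

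**3. A second set of assumptions** (90 per arm, different distributions), as chi-square / Fisher / two-sided Wilcoxon / one-sided Wilcoxon:

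- 60% users in both arms, user mean 4 to 2.8: 22/30/21/31%
- users 60% to 50%, user mean 4 to 3: 17/22/53/65%
- 90% users, user mean 5 to 3.5: 36/42/72/82%

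In the first of these Fisher is ahead of two-sided Wilcoxon.

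**4. Why rows cost power.** Suppose the whole signal lies in one ordered contrast, with the noncentrality that gives 80% one-sided power: (1.645 + 0.842)² = 6.18. Power at 0.05 is then 0.70 on 1 df (two-sided), 0.48 on 4 df, 0.33 on 10 df and 0.275 on 15 df, the most that rows 0 to 15 allow.

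**The case against.** The strongest reply is that little depends on this p-value. SAP 6.3.1 makes every non-primary result descriptive, direction can be read from the rows, and type I error is not inflated (3% for chi-square and 5% for Fisher with no effect). That stands and limits the weight of the point. It does not justify the test, because a descriptive p-value should still describe the stated objective.

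Other parts of the reply also stand:

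- **The one-sided conflict is not peculiar to this endpoint.** The same general wording of 6.3.1 conflicts with the chi-square tests of the four-level satisfaction items (SAP 10.2.4) and sits badly with baseline comparisons that have no expected direction.
- **The power figures rest on invented distributions.** They illustrate the loss and do not measure it.
- **Rejecting when the device is worse is not a fault.** Two-sided Wilcoxon does so too, in 80% of runs. The conflict is only with the one-sided rule.

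A reader might infer that the mock table breaks SAP 6.2, which for numbers lists: "For quantitative parameters: mean, standard deviation, median, Q1, Q3, extreme values (min and max". The documents do not support that. SAP 6.2 also provides counts and percentages for qualitative variables, and the mock table follows that branch. Treating a day count as qualitative is a questionable choice, not a broken rule.

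A reader might also infer that the frequency of use goes unreported, or that Table 14.2.3 supplies it. Neither holds. Row 0 of the mock table gives non-use, and hence any use. Table 14.2.3 covers all drugs by ATC class, and SAP 10.3 moves those ongoing from before the start date to previous medications.

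**Conclusion.** The point holds as a limited one. The planned test ignores the order of the days, has no one-sided form with more than two rows, and does not address the objective of reducing use. That follows from the documents alone.

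The loss of power is probable but rests on assumed distributions. In the first set Fisher had 17% to 42% power where two-sided Wilcoxon had 44% to 80% (general falls and fewer users). Where only the days among users fell, Fisher was level (20% v 20%) or ahead (30% v 21%). In a very sparse class no test helps. It would therefore be wrong to say that the planned test is always weaker.

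Nor do the documents support a reading that the trial's efficacy conclusion is at risk: the endpoint is secondary and the primary analysis does not use it. The change is worth making because it costs almost nothing.

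**What to change.** In SAP 10.2.3 and table 14.2.2.3.X:

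1. Compare days of use by a one-sided Wilcoxon-Mann-Whitney test, the test that SAP 10.2.2 already uses for symptom days.
2. Keep the count rows, and add the quantitative summaries of SAP 6.2 and the difference in mean days between arms.
3. Keep chi-square or Fisher, if wanted, only for any use versus none. That is a 2 × 2 table, for which a one-sided Fisher test exists.
4. Note under the table that subjects with V2 on D13 or D14, or who withdraw early, have fewer countable days. Early leavers otherwise look like low users. The present test shares this limitation.

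A bootstrap confidence interval for the mean difference, or showing counts only for very sparse classes, is optional.

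Align protocol 8.4, which under protocol section 10 needs a dated and signed amendment. Record the change and its reason in SAP section 12 before unblinding, and carry it into the report as protocol 8.10 requires. Section 12 shows that diary answers had already been looked at when it was written, so the entry should say that the change was made blind to treatment.

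The cost is one changed test statement and extra rows in six tables, with no new data. The number of p-values stays at six, or rises to at most twelve if the any-use comparison is also tested.

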#### 10.2.4. Subject general satisfaction in each group

The subject general satisfaction regarding ease of use, local tolerance and taste and efficacy at V2 in each group will be compared by means of chi-square or exact Fisher test for each of the three items.

The global subject feedback on treatment use (“will you recommend the prescribed treatment for treatment of acute rhinitis?”) in each group will be compared by means of chi-square or exact Fisher test.

Subjects will be analysed on the FAS.

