#### 7.1.4 Secondary Endpoints with methods and timing for assessing, recording and analysing variables

**--AUC of the symptoms sub-score (items 2-11) and Quality of Life sub-score (items 12-20) of the WURSS-21 during first 8 days**

**- Duration of cold symptoms** in both groups assessed by means of the WURSS-21.

For each item, the duration is defined as the number of symptomatic days between visit V1 and the first day the subject reports not to have this symptom for two consecutive days.

To be noticed that the duration may be censored at the end of study participation (visit V2). Should the patient have not ticked "not sick" for 2 consecutive days at the end of study visit, a WURSS-21 will be completed by the patient during the visit.

*Strictly Confidential*

- **Frequency and number of days of concomitant treatments use** that may affect common cold symptoms (antipyretics, systemic or local mucolytics, decongestants, antitussives, antibiotics).

By reducing duration of common cold symptoms, Healsea® Rescue\* will very likely reduce the use of common rescue medication. Concomitant treatments use will be reported in the e-diary by the patient throughout the study, validated by the investigator at the end of study visit before being reported in the e-CRF.

- **Subject satisfaction** regarding ease of use, efficacy, local tolerance and taste at end of study visit (V2) using a **4-points categorical scale** and of the **Global subject feedback** on treatment use ("will you recommend the prescribed treatment for treatment / prevention of acute rhinitis?").

Although subjective, these endpoints are pertinent because Healsea® Rescue\* is an OTC product which does not require physician prescription.

- **Safety:** Assessment of adverse events and incidents throughout the study in both groups. Adverse events/incidents will be reported in the e-diary by the patient, validated by the investigator at the end of study visit before being reported in the e-CRF.

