**Table 14.2.2.4. Subject general satisfaction in each group – Full Analysis Set**

	Healsea Rescue N=XX	Placebo N=XX
How would you characterize the use of the nasal spray?		
N	XX	XX
Missing	XX	XX
Not easy	XX (XX.X%)	XX (XX.X%)
Pretty easy	XX (XX.X%)	XX (XX.X%)
Easy	XX (XX.X%)	XX (XX.X%)
Very easy	XX (XX.X%)	XX (XX.X%)
Between-groups test	XXX (Chi-2/Fisher)	
How would you characterize the residual taste after spraying the prescribed treatment?		
N	XX	XX
Missing	XX	XX
Not pleasant	XX (XX.X%)	XX (XX.X%)
Neutral	XX (XX.X%)	XX (XX.X%)
Pleasant	XX (XX.X%)	XX (XX.X%)
Very pleasant	XX (XX.X%)	XX (XX.X%)
Between-groups test	XXX (Chi-2/Fisher)	
How would you characterize the cleansing and moistening of nasal mucosa with the prescribed treatment?		
N	XX	XX
Missing	XX	XX
No improvement	XX (XX.X%)	XX (XX.X%)
Slight improvement	XX (XX.X%)	XX (XX.X%)
Moderate improvement	XX (XX.X%)	XX (XX.X%)
Very clear improvement	XX (XX.X%)	XX (XX.X%)
Between-groups test	XXX (Chi-2/Fisher)	
Will you recommend the prescribed treatment for treatment of acute rhinitis?		
N	XX	XX
Missing	XX	XX
No	XX (XX.X%)	XX (XX.X%)
Yes	XX (XX.X%)	XX (XX.X%)
Between-groups test	XXX (Chi-2/Fisher)	

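### Three satisfaction items with four ordered answers are compared by an unordered chi-square or Fisher test, whose p-value ignores the order, has no direction and cannot follow the SAP's one-sided rule

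*SAP*

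**What the plan says.** Protocol 7.1.4 collects satisfaction with ease of use, efficacy, local tolerance and taste at V2 on a "4-points categorical scale". It adds a global question on whether the subject would recommend the treatment. Protocol 8.4 gives the analysis: "The subject general satisfaction in each group will be compared by means of chi-square test". It names Fisher's exact test for the global question. SAP 10.2.4 says that satisfaction at V2 "will be compared by means of chi-square or exact Fisher test for each of the three items", and allows either test for the global question.

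Mock Table 14.2.2.4 (SAP 13.2) shows the items and their answers:

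- use of the spray: not easy, pretty easy, easy, very easy;
- residual taste: not pleasant, neutral, pleasant, very pleasant;
- "How would you characterize the cleansing and moistening of nasal mucosa with the prescribed treatment": no, slight, moderate or very clear improvement;
- "Will you recommend the prescribed treatment for treatment of acute rhinitis": no or yes.

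The table gives n (%) per answer by group and one between-groups p-value per item. No trend test, rank test, ordinal model or effect estimate is planned for these items.

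Two other parts of the SAP bear on this. Section 2.2 lists as a secondary objective "To compare the subject overall assessment on efficacy of" the two sprays. Section 6.3.1 states: "All statistical analyses will be performed at the 0.05 global significance level (type I error rate), using one-sided tests". The same section makes only the primary result conclusive and treats all other p-values as informative.

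**The concern.** The answers run from worst to best, and the objective asks which spray subjects rate as more effective. A chi-square or Fisher test on a 2×4 table answers a different question: whether the two arms differ in any way across four unordered labels. A consistent move toward better ratings is spread over 3 degrees of freedom and is harder to detect. A small p-value does not by itself say which arm was rated higher. Nor can such a test be made one-sided, so the general rule in SAP 6.3.1 has no meaning for these three items.

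What is at stake is how informative the printed p-value is for the one graded item that asks about an effect of the spray. The primary conclusion is not touched.

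**Working it through.** **What the plan's own figures supply.** No power or sample size is stated for the satisfaction items. SAP 4 gives 90 evaluable subjects per group for the primary endpoint, and 180 / 0.9 = 200 randomised. The 90 per arm is used below. Everything else about the satisfaction distribution is assumed.

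**Step 1: order and direction.** Degrees of freedom are (2 − 1)(4 − 1) = 3. Take an illustrative table with 90 per arm: 12/28/32/18 against 6/22/36/26.

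- Column totals are 18/50/68/44, so the expected counts per arm are 9/25/34/22.
- Chi-square = 2 × (3²/9 + 3²/25 + 2²/34 + 4²/22) = 2 × (1 + 0.360 + 0.118 + 0.727) = 4.41; p = 0.220.
- The sum has the same value if the four columns are shuffled or the arms are swapped. It therefore holds no information on order or direction.

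Tie-corrected Wilcoxon on the same table:

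- Midranks are 9.5, 43.5, 102.5 and 158.5.
- Rank sum of the second arm = 6 × 9.5 + 22 × 43.5 + 36 × 102.5 + 26 × 158.5 = 8825. Its null expectation is 90 × 181 / 2 = 8145.
- Variance = (90 × 90 / 12) × [181 − Σ(t³ − t) / (180 × 179)] = 675 × (181 − 530268 / 32220) = 675 × 164.54 ≈ 111,067, so SD ≈ 333.3.
- z = 680 / 333.3 = 2.04; p = 0.041 two-sided and 0.021 one-sided.

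**Step 2: power under an assumed shift.** The assumption is proportional odds: odds of answering in category k or better on Healsea Rescue = OR × the same odds on placebo, for every k. For example, placebo 25/25/25/25% with OR 2.0 gives cumulative odds 3→6, 1→2 and 1/3→2/3, so the active arm is 14.3/19.0/26.7/40.0%.

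Five placebo distributions were assumed (25/25/25/25, 10/30/40/20, 20/30/30/20, 15/35/35/15 and 5/15/40/40%), with 40,000 simulated trials per scenario and 90 per arm. Ranges are over the five distributions. Fisher's test was not simulated.

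| OR | Chi-square, 3 df (%) | Wilcoxon two-sided 5% (%) | Loss (points) | Wilcoxon one-sided 5% (%) | Loss (points) |
|---|---|---|---|---|---|
| 1.0 | 4.7–5.1 | 4.8–5.0 | – | 5.0–5.1 | – |
| 1.5 | 19.4–21.4 | 30.1–32.7 | 10.7–11.6 | 42.2–44.8 | 22.8–23.5 |
| 1.75 | 34.8–38.4 | 51.0–54.6 | 16.2–16.8 | 63.4–66.9 | 28.5–29.2 |
| 2.0 | 50.5–56.0 | 68.3–73.1 | 16.9–17.8 | 78.7–82.6 | 26.2–28.2 |
| 2.25 | 65.4–70.8 | 81.0–85.1 | 14.2–15.6 | 88.5–91.3 | 20.5–23.1 |
| 2.5 | 76.5–81.8 | 89.1–92.4 | 10.4–12.6 | 93.9–96.0 | 14.2–17.4 |

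Analytic check: a 1-df two-sided 5% test with 80% power has noncentrality (1.960 + 0.842)² ≈ 7.85. The same noncentrality on 3 df gives 64.5%, a loss of 15.5 points.

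The two-sided column is the like-for-like comparison. The one-sided column combines two changes, use of the order and a lower critical value in the favoured direction.

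**Step 3: patterns that are not a uniform shift.** With 20/30/30/20% on placebo:

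| Other arm (%) | Chi-square | Wilcoxon two-sided |
|---|---|---|
| 10/30/30/30 | 42% | 49% |
| 20/15/45/20 | 61% | 20% |
| 30/20/20/30 | 60% | 5% |

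The second row is a move upward confined to the two middle answers, and the third adds answers at both extremes. In both, chi-square is clearly the stronger test.

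**The case against.** **The p-values are descriptive.** SAP 6.3.1 rests no conclusion on them, and these items were never powered. This stands and keeps the point minor. Even so, a p-value printed for information should address the question in the objective.

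**Other data serve the objective.** A reader might infer that the four-level ratings are all the trial has on subject-assessed efficacy. They are not. The yes/no recommendation item also informs it, and a 2×2 test loses no ordering. Of the three graded items, ease of use and taste are not efficacy ratings, so the effect on this objective falls on one item.

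**Direction is visible.** A reader might also infer that the analysis cannot show which spray was rated better. The percentages per answer show that descriptively. What is missing is a directional test or an estimate.

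**The power loss is conditional.** It assumes the kind of alternative that suits a rank test. Step 3 shows that the ranking can reverse, so no unconditional figure is justified.

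**The sidedness conflict is wider.** Chi-square or Fisher tests are also planned for the baseline COVID-19 test (SAP 8.6) and for days of medication use (SAP 10.2.3). The wording of SAP 6.3.1 is a general problem that a change in 10.2.4 does not cure.

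**One-sided testing of every item would be a mistake.** Protocol 5.2 expects itching and irritation with Healsea Rescue and no adverse effect with placebo, and SAP 10.2.4 groups local tolerance with taste. A one-sided test in favour of the device could not flag a worse rating there. The planned chi-square could. This stands and shapes the fix.

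**The SAP follows the protocol's pre-specified test.** It does, and SAP 12 describes subjects' answers in the past tense, so a change now comes after data have been seen, at least blinded. That is a reason to document and date the change, not to keep a test that discards the order.

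**Conclusion.** The point holds as a minor weakness in the choice of analysis. Three facts need no assumption: the answers are ordered, the planned test ignores that order and has no direction, and it cannot be one-sided as SAP 6.3.1 says all tests are.

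The size does need assumptions. With 90 per arm, a proportional-odds shift and OR 1.5 to 2.0, the loss is about 11 to 18 points against a two-sided 5% Wilcoxon test; extending to OR 2.5 makes it about 10 to 18. The documents give neither a distribution nor an effect for these items, and for patterns other than a uniform shift chi-square can be the better test. A rank test is still preferable because the objective is about which spray is rated better. The documents do not support saying that the objective is left without usable data, or that its result would be misleading.

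**What to change.** In SAP 10.2.4 and Table 14.2.2.4:

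- Compare each four-level item by a tie-corrected Wilcoxon-Mann-Whitney test, or equivalently a Cochran-Mantel-Haenszel row-mean-scores test.
- Report it two-sided, at least for ease of use and for taste/tolerance. A one-sided test under SAP 6.3.1 is suitable only for the cleansing and moistening item.
- Keep n (%) per answer, and keep chi-square or Fisher for the recommendation item.
- In SAP 12, record the departure from protocol 8.4 and any two-sided exception to SAP 6.3.1, dated before unblinding.

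The cost is a sentence or two in SAP 10.2.4, a label in the mock table and a short entry in SAP 12. No new data are needed, and SAP 10.2.2 already uses the same test for symptom durations. The price is less sensitivity to patterns that are not a consistent shift, which the retained percentages would still show.
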